#### **6.13.2.11. Diabetic Retinopathy Complications**

Results of the baseline dilated fundoscopic exam will be summarized by treatment. Any TEAE suspected of worsening retinopathy triggers a follow-up dilated fundoscopic exam. A summary of TEAEs suspected of worsening retinopathy and a summary of the results of the follow-up dilated fundoscopic exam will be summarized by treatment and PT. The cases with repeated fundoscopy during the course of the trial, based on clinical suspicion of worsening retinopathy that have either findings of de novo retinopathy or progression of retinopathy, and severe/serious adverse events from PTs defined in searching criteria in [Appendix 1](#) will be considered AESIs and summarized.

#### **6.13.2.12. Hepatobiliary Safety**

##### **6.13.2.12.1. Hepatobiliary Disorders**

The AE database will be searched using SMQs to identify events consistent with hepatobiliary disorders. Detailed searching criteria can be found in [Appendix 1](#). A summary by treatment and PT within SMQ will be provided. Severe/serious hepatobiliary disorders will be considered AESIs.

##### **6.13.2.12.2. Acute Gallbladder Disease**

The AE database will be searched using predefined SMQs to identify events consistent with acute gallbladder diseases. Detailed searching criteria for these AEs can be found in [Appendix 1](#). A summary by treatment and PT within SMQ will be provided. Severe/serious acute gallbladder diseases will be considered AESIs.

##### **6.13.2.12.3. Liver Enzymes**

Analyses for laboratory analyte measurements are described in Section [6.16](#). This section describes additional analyses of liver enzymes. In addition, the following will be provided by treatment group:

- A shift table of maximum to maximum alanine aminotransferase (ALT) measurement from baseline to postbaseline with the following categories:  $\leq$  upper limit of normal (ULN),  $>1$  to  $<3 \times$  ULN,  $\geq 3$  to  $<5 \times$  ULN,  $\geq 5$  to  $<10 \times$  ULN,  $\geq 10 \times$  ULN.
- A shift table of maximum to maximum aspartate transaminase (AST) measurement from baseline to postbaseline with the following categories:  $\leq$ ULN,  $>1$  to  $<3 \times$  ULN,  $\geq 3$  to  $<5 \times$  ULN,  $\geq 5$  to  $<10 \times$  ULN,  $\geq 10 \times$  ULN.
- Shift tables of maximum to maximum total bilirubin and direct bilirubin from baseline to postbaseline with the following categories:  $\leq$ ULN,  $>1$  to  $<2 \times$  ULN,  $\geq 2 \times$  ULN.
- Shift tables of serum alkaline phosphatase (ALP) from baseline to postbaseline with the following categories:  $\leq$ ULN,  $>1$  to  $<2 \times$  ULN,  $\geq 2 \times$  ULN.

Maximum baseline will be the maximum non-missing observation in the baseline period. The maximum value will be the maximum non-missing value from the postbaseline period. Planned and unplanned measurements will be included.

#### **6.13.2.13. Gastrointestinal Safety**

The time courses of prevalence and incidence (newly-occurring episodes) of nausea, vomiting, diarrhea, and combined will be plotted by treatment and maximum severity.

The maximum severity and duration of treatment-emergent nausea, vomiting, diarrhea, and combined through the end of the study will be summarized by treatment.

The PTs in the gastrointestinal SOC will be used to identify gastrointestinal AEs. The incidence of the resulting TEAEs will be summarized by treatment and PT. Preferred Terms with severe/serious cases in the gastrointestinal SOC will be considered AESIs.

#### **6.13.2.14. Acute Renal Events**

Laboratory measures related to renal safety will be analyzed as specified for laboratory measurements in Section 6.16.

Two shift tables examining renal function will be created. A min-to-min shift table of estimated glomerular filtration rate (eGFR) estimated by the Chronic Kidney Disease Epidemiology Collaboration (CKD-EPI) equation with units ml/min/1.73m^2, using categories (<45, ≥45 to <60, ≥60 to <90, and ≥90 mL/min/1.73m^2). A max-to-max shift table of urine albumin-to-creatinine ratio (UACR), using the categories UACR <30 mg/g, 30 mg/g ≤ UACR ≤ 300 mg/g, UACR >300 mg/g (respectively, these represent normal, microalbuminuria, and macroalbuminuria).

The AE database will be searched using SMQs of acute renal failure and chronic kidney disease to identify events consistent with acute renal events. The incidence of the resulting TEAEs will be summarized by treatment and PT. Detailed searching criteria can be found in [Appendix 1](#). Severe/serious acute renal events will be considered AESIs.

#### **6.13.2.15. Dehydration**

The AE database will be searched using an SMQ of dehydration to identify events consistent with dehydration. Detailed searching criteria can be found in [Appendix 1](#). Severe/serious dehydration events will be considered AESIs.

#### **6.13.2.16. Metabolic Acidosis, Including Diabetic Ketoacidosis**

The AE database will be searched using MedDRA PT to identify events consistent with metabolic acidosis, including diabetic ketoacidosis. Detailed searching criteria can be found in [Appendix 1](#). The incidence of the resulting TEAEs will be summarized by treatment and PT. Severe/serious metabolic acidosis, including diabetic ketoacidosis, will be considered an AESI.

#### **6.13.2.17. Amputation/Peripheral Revascularization**

The AE database will be searched using MedDRA PT to identify events consistent with amputation or peripheral revascularization. The incidence of the resulting TEAEs will be

summarized by treatment and PT. Amputation/peripheral revascularization will be considered an AESI.

#### 6.13.2.18. Major Depressive Disorder/Suicidal Ideation

The AE database will be searched using SMQs to identify events consistent with major depressive disorder or suicidal ideation. Detailed searching criteria can be found in [Appendix 1](#). The incidence of the resulting TEAEs will be summarized by treatment and PT. Severe/serious major depressive disorder/suicidal ideation or behavior will be considered an AESI.

#### 6.13.2.19. Treatment of Overdose

A listing of patients reporting overdosing of tirzepatide will be provided as a protocol deviation.

### 6.14. Vital Signs

Descriptive summaries by treatment and by nominal visit will be provided for baseline and postbaseline values as well as change from baseline values. If 2 records are taken at the same visit, they will be averaged prior to being used for data summaries and analyses.

A MMRM using REML will be used to fit the changes from baseline in vital signs at all scheduled postbaseline visits. The model will include country/pooled country, baseline HbA1c ( $\leq 8.5\%$ ,  $> 8.5\%$  [ $\leq 69$ ,  $> 69$  mmol/mol]), baseline concomitant oral antihyperglycemic medication (metformin alone vs metformin plus an SGLT-2i), treatment group, visit, and treatment-by-visit interaction as fixed effects, and baseline value of the dependent variable as a covariate. To model the covariance structure within patients, the unstructured covariance matrix will be used.

Counts and percentages of patients with abnormal sitting systolic blood pressure (BP), sitting diastolic BP, and pulse will be presented by treatment. The criteria for identifying patients with treatment-emergent vital sign abnormalities are stated in [Table GPGH.6.4](#).

**Table GPGH.6.4. Categorical Criteria for Abnormal Blood Pressure and Pulse Measurements**

Parameter	Low	High
Systolic BP (mm Hg) (Supine or sitting – forearm at heart level)	$\leq 90$ and decrease from baseline $\geq 20$	$\geq 140$ and increase from baseline $\geq 20$
Diastolic BP (mm Hg) (Supine or sitting – forearm at heart level)	$\leq 50$ and decrease from baseline $\geq 10$	$\geq 90$ and increase from baseline $\geq 10$
Pulse (bpm) (Supine or sitting)	$< 50$ and decrease from baseline $\geq 15$	$> 100$ and increase from baseline $\geq 15$

### 6.15. Electrocardiograms

Summary statistics by treatment and by nominal visit will be provided for ECG parameters (heart rate, PR, QRS, QT, and QT corrected using Fredericia's correction factor [QTcF]). When the QRS is prolonged (for example, a complete bundle branch block), QT and QTc should not be

used to assess ventricular repolarization. Thus, for a particular ECG, the following will be set to missing (for analysis purposes) when QRS is  $\geq 120$  msec: QT and QTcF.

The criteria for identifying patients with treatment-emergent quantitative ECG abnormalities is based on [Table GPGH.6.5](#).

In addition, the percentage of patients with QT greater than 500 msec will be summarized, and the percentage of patients with QTcF greater than 500 msec will be summarized.

The percentage of patients who experienced a treatment-emergent increase from baseline in QTcF interval of greater than 30 msec, 60 msec, or 75 msec at any time will be summarized. The maximum value during the study follow up will be analyzed. Planned and unplanned measurements will be included.

Treatment-emergent qualitative ECG abnormalities are defined as qualitative abnormalities that first occurred after baseline. A listing of abnormal qualitative ECGs will be created.

**Table GPGH.6.5. Selected Categorical Limits for ECG Data**

Parameter	Low		High	
	Males	Females	Males	Females
Heart Rate (bpm)	<50 and decrease $\geq 15$	<50 and decrease $\geq 15$	>100 and increase $\geq 15$	>100 and increase $\geq 15$
PR Interval (msec)	<120	<120	$\geq 220$	$\geq 220$
QRS Interval (msec)	<60	<60	$\geq 120$	$\geq 120$
QTcF (msec)	<330	<340	>450	>470

## 6.16. Clinical Laboratory Evaluation

All laboratory data will be reported in the International System of Units. Selected laboratory measures will also be reported using conventional units. Values that are outside of reference ranges will be flagged as high (H) or low (L) in the listings. Descriptive summaries by treatment and by nominal visit will be provided for the baseline and postbaseline values as well as the change from baseline values.

Observed and change from baseline values for each visit will be displayed in box plots for patients who have both a baseline and a postbaseline planned measurement. Unplanned measurements will be excluded from box plots.

A shift table will be provided including unplanned measurements. The shift table will include the number and percentage of patients within each baseline category (low, normal, high, or missing) versus each postbaseline category (low, normal, high, or missing) by treatment. The proportion of patients shifted will be compared between treatments using Fisher's exact test.

For qualitative laboratory analytes, the number and percentage of patients with normal and abnormal values will be summarized by treatment.

A listing of abnormal findings will be created for laboratory analyte measurements, including qualitative measures. The listing will include patient ID, treatment group, laboratory collection date, study day, analyte name, and analyte finding.

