## 10.3. Statistical Analyses

### 10.3.1. General Statistical Considerations

Statistical analysis of this study will be the responsibility of Lilly or its designee. Any change to the data analysis methods described in the protocol will require an amendment ONLY if it changes a principal feature of the protocol. Any other change to the data analysis methods described in the protocol, and the justification for making the change, will be described in the statistical analysis plan (SAP) or the clinical study report (CSR). Additional exploratory analyses of the data may be conducted as deemed appropriate.

Unless otherwise noted, all tests of treatment effects will be conducted at a 2-sided alpha level of 0.05, and the confidence interval (CI) will be calculated at 95%, 2-sided. In statistical summaries and analyses, patients will be analyzed as randomized.

There will be 2 estimands of interest in comparing efficacy of LY3298176 doses with insulin degludec. First estimand, the “efficacy” estimand, represents efficacy prior to discontinuation of study drug without confounding effects of antihyperglycemic rescue therapy. Second estimand, the “treatment-regimen” estimand, represents the efficacy irrespective of adherence to study drug or initiation of rescue antidiabetic drugs.

The primary efficacy assessment, guided by the “efficacy” estimand, will be conducted using the efficacy analysis set (EAS). The primary efficacy assessment, guided by the “treatment-regimen” estimand, will be conducted using the full analysis set (FAS). As they are intended for different purposes, no multiplicity adjustments will be made for conducting 2 primary efficacy assessments.

Unless specified otherwise, safety assessments will be guided by an estimand comparing safety of LY3298176 doses with insulin degludec irrespective of adherence to study drug or initiation of antihyperglycemic rescue therapy. Thus, safety analysis will be conducted using the SAS. Selected safety analyses will be conducted after excluding data on rescue therapy.

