#### **10.3.4.4. Central Laboratory Measures, Vital Signs, and Electrocardiograms**

Values and change from baseline to postbaseline values of central laboratory measures, vital signs, and selected ECG parameters will be summarized at each scheduled visit. The analysis model to make comparisons among treatment groups relative to continuous change from baseline values assessed over time will be an MMRM similar to the primary efficacy analysis and with baseline measurement as a covariate. An unstructured covariance structure will model relationship of within-patient errors.

The percentages of patients with TE abnormal, high, or low laboratory measures at any time will be summarized and compared between treatment groups by using Fisher's exact test. A TE abnormal value is defined as a change from normal value at baseline to a value greater than the high limit at any time during Periods II and III. A TE low result is defined as a change from a value greater than or equal to the low limit at baseline to a value less than the low limit at any time during Periods II and III. The high and low limits will be provided in the SAP.

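### SAP 6.16 tests an undefined, undirected proportion of patients shifted and does not carry over the protocol's treatment-emergent high and low laboratory comparisons

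*SAP*

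**What the plan says.** SAP 6.16 (Clinical Laboratory Evaluation) plans a shift table that crosses "each baseline category (low, normal, high, or missing) versus each postbaseline category (low, normal, high, or missing) by treatment". One inferential sentence follows: "The proportion of patients shifted will be compared between treatments", by Fisher's exact test. The section does not define *shifted*, give a direction, say how the missing category is handled, or say which postbaseline value sets a patient's category. It says that values outside the reference ranges are flagged in listings.

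Protocol 10.3.4.4 plans a different categorical analysis: "The percentages of patients with TE abnormal, high, or low laboratory measures at any time will be summarized and compared between treatment groups", also by Fisher's exact test. Its events have a direction. The low event is described as "change from a value greater than or equal to the low limit at baseline to a value less than the low limit", counted whenever it occurs in Periods II and III. The high-side event, which the protocol labels treatment-emergent abnormal, runs from a normal baseline to above the high limit. The protocol adds: "The high and low limits will be provided in the SAP".

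SAP 6.16 neither repeats this comparison nor says which limits apply to it. Protocol 10.3.1 and SAP 6.2 both say that changes to protocol methods, with their justification, will be described in the SAP or the clinical study report. SAP 6.16 gives no such reason. SAP section 3 does not mention the matter either, although that list covers major changes between SAP versions, not departures from the protocol.

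**The concern.** The safety question is whether more patients become abnormal on tirzepatide than on degludec. A single proportion of patients who changed category answers another question. High to normal counts the same as normal to high, and a move to or from missing may count as well. Its null hypothesis is an equal chance of any category change.

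Two errors become possible. A drug that only normalises an analyte can give a significant result in a safety table. A real excess of new abnormalities can be diluted by background normalisation, or offset if the harmed arm also normalises less often. Dilution is the more ordinary case, because it needs no difference between arms in improvement. At stake is the reading of routine laboratory safety, not the primary endpoint.

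**Working it through.** **Inputs.** The plan states no power or rate for this test, so there is no figure of its own to reproduce. SAP 5.2 gives 1420 patients in four equal arms: 1420 / 4 = 355 per arm. Protocol 10.3.1 sets the level: "all tests of treatment effects will be conducted at a 2-sided alpha level of 0.05" unless otherwise noted. SAP 6.6 makes no multiplicity adjustment for safety. All event rates below are assumptions, expressed as percentages of all 355 patients in an arm.

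**Method.** Let w be the proportion with a new high and i the proportion who normalise. On the plain reading, the shifted proportion is s = w + i. Exact power of the two-sided Fisher test is the sum over x and y of Bin(x; 355, p₁) × Bin(y; 355, p₂), taken over all pairs (x, y) with a Fisher p-value of at most 0.05. It is computed once with p = s (any shift) and once with p = w (new highs only).

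**Step 1: no harm, w = 4% in both arms.** The new-high test rejects 3% of the time. Tirzepatide is given first.

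| Improvement i | Shifted s | Any-shift test rejects |
|---|---|---|
| 6% v 5% | 10% v 9% | 6% |
| 7% v 5% | 11% v 9% | 12% |
| 10% v 5% | 14% v 9% | 50% |
| 12% v 5% | 16% v 9% | 78% |
| 15% v 5% | 19% v 9% | 97% |

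**Step 2: harm, w = 10% v 4%.** The new-high test has 86% power.

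| Improvement i | Shifted s | Any-shift power |
|---|---|---|
| 2% v 2% | 12% v 6% | 77% |
| 5% v 5% | 15% v 9% | 65% |
| 10% v 10% | 20% v 14% | 53% |
| 5% v 8% | 15% v 12% | 18% |
| 5% v 11% | 15% v 15% | 4% |

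The last row is built to cancel exactly: 10 + 5 = 4 + 11 = 15.

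**Step 3: dilution by baseline prevalence.** Let b be the share of patients abnormal at baseline. Suppose 40% of them normalise in both arms, and 12% v 5% of baseline-normal patients become abnormal. Then s = 0.40b + (1 − b) × 0.12 or 0.05, and w = (1 − b) × 0.12 or 0.05. For b = 20%:

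- s = 0.08 + 0.096 = 17.6% v 0.08 + 0.04 = 12.0%
- w = 9.6% v 4.0%

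| b | Any-shift power | New-abnormality power | Loss (points) |
|---|---|---|---|
| 10% | 71% | 87% | 16 |
| 20% | 52% | 82% | 30 |
| 30% | 36% | 75% | 39 |
| 40% | 25% | 68% | 43 |

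**The case against.** The best defence is that *shifted* is undefined, so pooling is a reading of the text and not something the SAP says. The sponsor may mean worsening only. This stands as a limit on the claim, but it leads to the same edit: if only worsening counts, 6.16 must say so.

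A reader might infer that the SAP deliberately replaced the protocol's test. The documents do not support that. No deletion is described, and the protocol comparison can be read as still planned. What is shown is a comparison that was not carried over and needs reconciling.

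A reader might also infer that this is the only between-arm categorical test for laboratory data. That is not supported either. Protocol 10.3.4.4 plans its own test, and SAP 6.13 makes Fisher's exact test the default for categorical safety responses. That default names no laboratory response, however, so it does not clearly restore the protocol's comparison.

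The mitigation is real. SAP 6.13 models mean change from baseline, which has a direction. Pancreatic enzymes (6.13.2.3.1), calcitonin (6.13.2.5.1), liver enzymes (6.13.2.12.3) and eGFR and urinary albumin/creatinine ratio (6.13.2.14) have their own threshold or directional shift tables. The 6.16 table prints every cell, so a reader can see where a difference arises. But a mean-change model does not count patients who become abnormal, and those analyte-specific sections name no between-arm test of new abnormalities.

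**Conclusion.** The point holds as a mismatch between the protocol and SAP 6.16, combined with a tested quantity that is undefined and, on its plain reading, undirected. Under the assumed rates with 355 per arm, equal 10% normalisation reduces power for new highs of 10% v 4% from about 86% to about 53%. In the prevalence scenarios the loss is 16 to 43 points.

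The extreme results should not be read as expected behaviour. Power of 4% needs exact cancellation, and false flags of 50% to 97% need improvement to double or triple. With improvement of 6% or 7% v 5%, the false-flag rate is about 6% or 12%. The documents give no laboratory event rates, so no single figure can be called the plan's own. All figures also assume that all 355 patients per arm are evaluable and that any change between low, normal and high counts as a shift. The change is worth making because it restores the question the protocol asked and costs very little. It has no bearing on the primary or key secondary analyses.

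**What to change.** Amend SAP 6.16 as follows.

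- Keep the full shift table as a descriptive display and remove the test on the proportion shifted.
- For each analyte, test treatment-emergent high and treatment-emergent low separately by Fisher's exact test, each tirzepatide dose v degludec.
- Use as denominator the patients at risk for that event who have a non-missing baseline and at least one postbaseline value, so that missing is never an event. Classify on any postbaseline value in Periods II and III, as the protocol does.
- State that the reference-range limits used for the listing flags are the high and low limits the protocol promised.
- Use the protocol's baseline conditions: normal for the high event, at or above the low limit for the low event. If the sponsor prefers *not high at baseline* for the high event, declare and justify it as a change, because it would also count patients who go from low to high.

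If the protocol's comparison was dropped on purpose, the SAP should say so and give the reason. The cost is a few lines of text and no new data. The downside is two tests per analyte instead of one, with no multiplicity adjustment planned for safety.

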## **6.17. Health Outcomes**

The patient-reported outcome questionnaires will be completed by the patients at baseline and at 52 weeks (or early termination visit prior to 52 weeks). These include use of the mITT population on the EAS, and use of a 2-sided alpha level of 0.05 and a 2-sided 95% CI for pairwise comparisons.

No multiplicity adjustment will be made in the evaluation of health outcome measures. Item-level missingness is dealt with as per the instrument developers' instruction.

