Patients who stop the study drug permanently will receive another glucose-lowering intervention (Section 7.4.2) and will continue participating in the trial according to the protocol to collect all planned efficacy and safety measurements.

Patients discontinuing from the investigational product prematurely for any reason should complete AE and other follow-up procedures per Section 2 Schedule of Activities, Section 9.2 Adverse Event, and Section 9.4 Safety of this protocol.

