**Table GPGH.6.1. Description of Analysis Datasets**

Analysis Set	Description
Screened population	All participants who sign informed consent
Randomized population	All patients who are randomly assigned a treatment arm
modified intention-to-treat (mITT) population	All randomly assigned participants who are exposed to at least 1 dose of study drug. In the event of a treatment error, participants will be analyzed according to the treatment they were randomized.
Efficacy analysis set (EAS)	Data obtained during Study Period II from the mITT population, excluding patients discontinuing study drug due to inadvertent enrollment and data after initiating rescue antihyperglycemic medication or stopping study drug (last dose date +7 days).
Full analysis set (FAS)	All available data obtained during Study Period II from mITT, excluding patients discontinuing study drug due to inadvertent enrollment, regardless of adherence to study drug or initiation of rescue antihyperglycemic medication.
Safety analysis set (SS)	Data obtained during Study Periods II or III from the mITT population, regardless of adherence to study drug or initiation of rescue antihyperglycemic medication.

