#### **6.12.1.2. The Analysis Relative to the Treatment Regimen Estimand**

The analysis will be conducted utilizing HbA1c data in the FAS at baseline and at the 52-week visit with the aid of an ANCOVA. The response variable will be the primary measure and model terms will include treatment, country/pooled country, and baseline concomitant oral antihyperglycemic medication use (metformin alone versus metformin plus an SGLT-2i) as fixed

effects and baseline HbA1c as a covariate. The ANCOVA analysis will be conducted with multiple imputation of missing primary measures (see Section 6.12.1.3 for details) and statistical inference over multiple imputation of missing data guided by Rubin (1987).

With the aid of the ANCOVA analysis 2-sided 97.5% CI for mean change in HbA1c from baseline to the 52-week visit for (10 mg tirzepatide – insulin degludec) as well as for (15 mg tirzepatide – insulin degludec) will be derived. If the upper limits of the CI are  $\leq 0.3\%$ , then the respective dose of tirzepatide (10 mg and/or 15 mg) will be declared noninferior to insulin degludec relative to change in HbA1c from baseline.

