## Secondary and Exploratory Efficacy Measures Not Controlled for Type 1 Error

Objective	Relative to the efficacy measure:	Analysis Conducted in a manner similar to:	Additional Information
	Proportion of patients achieving weight loss from baseline of $\geq 15\%$ .	6.12.2.3	Use baseline HbA1c strata as a fixed effect in place of baseline HbA1c as a covariate. Use baseline weight as a covariate.
To compare tirzepatide 5 mg, 10 mg, and 15 mg to insulin degludec at 52 weeks	The various Diabetes Treatment Satisfaction Questionnaire change (DTSQc) scores (see Section 6.17.4 for more details).	6.12.1.2	Use baseline HbA1c strata as a fixed effect in place of baseline HbA1c as a covariate. Use baseline DTSQs score as a covariate.
	Changes from baseline in the Impact of Weight on Self-Perceptions Questionnaire (IW-SP) scores.	6.12.1.2	Use baseline HbA1c strata as a fixed effect in place of baseline HbA1c as a covariate. Use baseline IW-SP score as a covariate.
	Changes from baseline in the Ability to Perform Physical Activities of Daily Living (APPADL) scores.	6.12.1.2	Use baseline HbA1c strata as a fixed effect in place of baseline HbA1c as a covariate. Use baseline APPADL score as a covariate.
Exploratory Analyses			
To compare tirzepatide 5 mg, 10 mg, and 15 mg with insulin degludec for the following:	Change from baseline in lipid parameters (total cholesterol, HDL, VLDL, TG).	6.12.1	Use baseline HbA1c strata as a fixed effect in place of baseline HbA1c as a covariate. Use corresponding baseline lipid parameter as a covariate.
	Change from baseline in BMI.	6.12.1	Use baseline HbA1c strata as a fixed effect in place of baseline HbA1c as a covariate. Use corresponding baseline BMI as a covariate.
	Change from baseline in waist circumference.	6.12.1	Use baseline HbA1c strata as a fixed effect in place of baseline HbA1c as a covariate. Use corresponding baseline waist circumference as a covariate.
	Changes from baseline in the European Quality of Life – 5 dimensions (EQ-5D) index and visual analog scale (VAS) scores.	6.12.1.2	Use baseline HbA1c strata as a fixed effect in place of baseline HbA1c as a covariate. Use baseline EQ-5D score as a covariate.

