### **6.17.4. Diabetes Treatment Satisfaction Questionnaire**

The Diabetes Treatment Satisfaction Questionnaire (DTSQ) contains 8 items (conceptually the same items in the status [DTSQs] and change [DTSQc] versions). Six items (1, and 4 through 8)

are summed to produce a measure of treatment satisfaction and the 2 remaining items (2 and 3) are treated individually to assess, respectively, the perceived frequency of hyperglycemia and hypoglycemia. The DTSQs is used to assess treatment satisfaction at baseline and the DTSQc is used to assess relative change in satisfaction from baseline at week 52 or early termination.

Descriptive summaries will be provided at baseline (DTSQs only) and at 52 weeks (DTSQc only) for the perceived hyperglycemia item, perceived hypoglycemia item, and 6-item overall satisfaction score.

Treatment comparisons in the DTSQc at Week 52 will be analyzed using an ANCOVA model with model terms of treatment, country/pooled country, baseline HbA1c ( $\leq 8.5\%$ ,  $> 8.5\%$  [ $\leq 69$ ,  $> 69$  mmol/mol]), and baseline concomitant oral antihyperglycemic medication use (metformin alone versus metformin plus an SGLT-2i) as fixed effects, and baseline DTSQs score as a covariate. The analyses will be conducted for the perceived hyperglycemia item, perceived hypoglycemia item, and 6-item overall satisfaction score.

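### SAP 6.17 puts the patient-reported outcomes on the EAS while Table GPGH.6.2 and 6.12 point to the FAS; following 6.17 discards Week 52 scores from patients who stopped drug or were rescued but stayed in the trial

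*SAP*

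**What the plan says.** **Analysis set in 6.17.** For the health outcomes, SAP 6.17 states: "These include use of the mITT population on the EAS". Under SAP Table GPGH.6.1 the EAS leaves out data collected after rescue starts or more than 7 days after the last dose.

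**Pointer in Table GPGH.6.2.** The row for "The various Diabetes Treatment Satisfaction Questionnaire change (DTSQc) scores", and the rows for IW-SP, APPADL and EQ-5D, cite 6.12.1.2 as the analysis to resemble. That section covers the treatment-regimen estimand and uses data "in the FAS at baseline and at the 52-week visit with the aid of an ANCOVA".

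**General rules.** SAP 6.2 applies two estimands to the primary and secondary efficacy objectives. SAP 6.12 puts all efficacy assessments for the FDA on the FAS, without imputation for objectives outside type 1 error control, and reserves the EAS for publications and other purposes.

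**Timing.** SAP 6.17 schedules the questionnaires at baseline and Week 52, or at an early termination visit before then. SAP 6.17.4 says "the DTSQc is used to assess relative change in satisfaction from baseline at week 52 or early termination", but its treatment comparison is at Week 52.

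**Missing scores.** SAP 6.12.4 says other secondary and exploratory measures are not imputed. SAP 6.17.1 (EQ-5D) and 6.17.2 (IW-SP) nevertheless specify LOCF; 6.17.3 (APPADL) and 6.17.4 (DTSQ) do not.

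**Follow-up.** Under protocol 8.1.1, patients who permanently stop drug "will continue participating in the trial according to the protocol to collect all planned efficacy and safety measurements".

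**EQ-5D.** It is an exploratory endpoint, and protocol 10.3.3.3 places all exploratory efficacy analyses on the EAS.

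**The concern.** Two parts of the SAP name different analysis sets for the same endpoints, and the difference matters more here than for HbA1c. HbA1c is measured at many visits, so a patient who stops drug midway still contributes earlier on-drug values to the MMRM. A questionnaire has one scheduled postbaseline point and is analyzed by ANCOVA. If the patient stopped drug well before Week 52 or was rescued, the EAS removes that one score and no earlier postbaseline score replaces it.

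What remains is a comparison of patients selected by what happened after randomization in an open-label trial. Stopping and rescue may be related to how satisfied a patient is and may differ between arms. Because the text supports either set, the choice could also be made at reporting, after open-label data have accrued.

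**Working it through.** **1. Which scores each set keeps at Week 52**

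| Patient | EAS (6.17) | FAS (6.12.1.2, 6.12) |
|---|---|---|
| On drug, not rescued | kept | kept |
| On drug, rescued earlier | dropped | kept |
| Stopped drug more than 7 days earlier, still in trial | dropped | kept |
| Left the trial before Week 52 | no Week 52 score | no Week 52 score |

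The early termination route does not recover the second and third rows. Footnote b of the protocol's Schedule of Activities reserves that visit for patients unable or unwilling to continue in the study. It can supply an EAS score for someone in the fourth row, if the visit falls within 7 days of the last dose and before any rescue. Where LOCF applies, the second- and third-row patients have no postbaseline EAS score to carry forward, and the SAP does not say whether baseline would be carried.

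**2. The plan's own figure**

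The documents give no power or effect size for the questionnaires. The only planning rate for stopping or rescue is in SAP 5.2 and protocol 10.1: 355 per arm, at most 28% rescued or stopping drug, SD 1.1, effect 0.35, superiority margin 0.05, two-sided alpha 0.025 per dose, power at least 90%.

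- Evaluable per arm: 355 × 0.72 = 255.6.
- Net effect: 0.35 − 0.05 = 0.30. Standard error: 1.1 × √(2/255.6) = 0.0973.
- Per dose: 0.30/0.0973 − 2.241 = 0.84, so power is 80.0%.
- At least one of two doses (correlation 0.5 from the shared control): 91.3%.

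The stated 90% is reproduced on the and/or reading, so 28% is used here as the plan's own ceiling.

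**3. How many scores could be affected**

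0.28 × 355 = 99.4 per arm, or 4 × 99.4 = 397.6 of 1420 overall, leaving 255.6 per arm. This is an upper limit. The 28% is itself a ceiling, and some of those patients will leave the trial and have no Week 52 score under either set.

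**4. Precision, in SD units**

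95% half-width for a pairwise difference = 1.96 × √(2/n).

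- EAS at the ceiling: 1.96 × √(2/255.6) = 0.173.
- Complete FAS: 1.96 × √(2/355) = 0.147.

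**5. Possible shift between the two analyses**

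If a share d of an arm is excluded and those patients score g SD below the patients kept, the kept mean exceeds the all-patient mean by d × g. With the same g in both arms, the EAS difference minus the FAS difference is g × (d1 − d0), where 1 is tirzepatide and 0 is degludec. The documents give neither g nor separate exclusion rates, so these are assumptions:

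| d1 vs d0 | g = 0.25 | g = 0.5 | g = 1.0 |
|---|---|---|---|
| 28% vs 28% | 0 | 0 | 0 |
| 18% vs 8% | 0.025 | 0.05 | 0.10 |
| 28% vs 8% | 0.05 | 0.10 | 0.20 |

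The sign reverses if degludec loses more patients, or if excluded patients score higher than those kept.

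**The case against.** The strongest reply is that the SAP already plans the missing analysis. DTSQ, IW-SP and APPADL are secondary objectives, 6.2 gives secondary efficacy objectives both estimands, and 6.12 puts FDA assessments on the FAS. On that reading 6.17 merely fails to repeat the general rule. This stands in part: a reader should not infer that the SAP rules out a FAS analysis. But 6.17 is the specific rule for these endpoints, and it names only the EAS. A programmer following it would not produce the FAS result.

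The column in Table GPGH.6.2 asks only for a similar analysis, so 6.12.1.2 may be cited for its ANCOVA model alone. That is possible, and the sentence in 6.17 has no clear antecedent. Both points show that the text does not settle the analysis set.

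An on-treatment estimand for satisfaction with the assigned drug is also defensible, and these endpoints are outside type 1 error control. Both are true. They bear on which result leads, not on whether the FAS result should be available.

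A reader might infer that the EAS favors tirzepatide, because patients who stop for gastrointestinal intolerance would be dissatisfied. The documents do not support that. Patients who stop receive another glucose-lowering treatment (protocol 8.1.1), and DTSQ asks about satisfaction with diabetes treatment (protocol 9.9.1), so an off-drug score may reflect the replacement. No differential stopping rate or score gap is given, and the 28% applies to each arm alike.

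**Conclusion.** The conflict is real and affects results. Following 6.17 drops Week 52 scores that the protocol sets out to collect, and with one scheduled postbaseline point the ANCOVA cannot make up for them. The result is close to an on-treatment completer comparison.

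At most about 99 of 355 patients per arm are affected, assuming the 28% ceiling is reached and all of them stay to Week 52. The size and direction of any bias are unknown. The 0 to 0.20 SD range is illustrative, and the shift is zero when exclusion and score gap are equal between arms.

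It would go too far to say that satisfaction is scored only in patients who stayed on drug. The EAS keeps scores up to 7 days after the last dose, which can include some early termination scores, and it also removes later scores from rescued patients who are still on drug. Moving every questionnaire to the FAS as its main set would also go too far, because protocol 10.3.3.3 assigns EQ-5D to the EAS. The point warrants a SAP change but does not touch the primary or key secondary conclusions.

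**What to change.** Revise SAP 6.17 as follows:

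- For DTSQc, IW-SP and APPADL, specify the ANCOVA on the FAS, using all Week 52 questionnaires regardless of adherence or rescue. Report the EAS version beside it, labelled as on-treatment.
- Keep EQ-5D on the EAS, in line with protocol 10.3.3.3, and add a FAS run as sensitivity.
- State whether and how early termination scores enter each analysis, in particular the Week 52 comparison of DTSQc.
- Reconcile LOCF in 6.17.1 and 6.17.2 with the no-imputation rule in 6.12.4, and say whether baseline can be carried forward.
- Align Table GPGH.6.2 with the result, so that each questionnaire has one stated analysis set and estimand per analysis.

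The cost is SAP wording and one extra run per questionnaire; no new data collection is needed. Off-drug scores may dilute an on-drug effect in the FAS result, but the EAS version still shows that effect.
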